After enrollment, CHWs will introduce themselves and ask for the introduction of contacts and it is at this time when a contacts master list will be created. Index patients will then be asked the influence questions. The questions will be asked in two steps, once to capture the number and once to capture the name. The other CHW will go head to conduct routine TB contact investigation activities.

b) Household contact screening interview

After household contact enrolment, each contact will undergo a short interview. This interview will capture age, gender, occupation (if applicable), income (if applicable), education in years, relationship to index patient, history of testing for HIV, month and year of last HIV test, and self-reported symptoms of TB (including cough, subjective fever, or weight loss).

The short (13-item) version of the Van Rie TB- and HIV-related stigma scales will be administered immediately prior to TB screening, as well as at the conclusion of the visit. We will ask the index patient to share the number of rooms in the dwelling, the number of windows in the dwelling, and the number of individuals (including children) who dwell there. All screening interview components will be conducted by a CHW. Screening interview components are identical for all study groups.

c) HIV testing procedures

Working in teams of two, CHWs will provide household contact investigation services, including offering oral HIV testing. One CHW will lead and accompany each HIV test while a colleague leads other household members through TB screening.

To begin, the CHW responsible for offering HIV testing will individually invite the client to a place apart from the others. S/he will detail the process of HIV testing in Luganda and/or English, per client preference. A pictorial guide may be used to help walk the client through each step of the process using a Luganda- or English-language guide. The CHW will then provide pre-test counselling.

Consenting household contacts who choose to test for HIV will swab their own gums. CHWs will be fully trained to provide HIV counselling and support throughout all testing procedures.

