Administering the oral test The CHW will open the OraQuick test packet in front of the consenting household contact and hand them the test swab. The CHW will remain with the client to directly supervise the test. Consenting clients will be directed to use the test swab to gently swipe once around their upper gums and once around their lower gums. Either side of the swab can be used. The swab will then be placed in the testing liquid for no more than 40 minutes. After 20 minutes has passed, the CHW will assist the participant in reading their HIV testing results. Procedures regarding HIV test results are outlined below. While awaiting test results, the CHW will provide basic education to the contact on HIV and/or TB and answer health related questions that the contact may have.

HIV test results If the test is negative (one line next to the C and NO line in any form next to the T), the CHW will provide HIV counselling and support. If the HIV test is positive OR unconfirmed (one line next to BOTH the C and T regardless of how faint OR no line shown in window at all), the CHW will provide HIV counselling and support as well as a referral to the health centre for confirmatory capillary blood testing.

Referral protocol Regardless of study arm, if the HIV test is positive or unconfirmed, the CHW will refer the client to the health center for evaluation and care using a referral slip. First, the CHW will explain the result in direct, simple language. For a positive result, they will explain: "The test shows you have HIV. You need to go to the ART clinic. I will support you." The CHW will give the patient a referral slip and phone number to call upon reaching the clinic. Finally, the CHW will engage the client in planning to link to care by suggesting a specific day and time to present at the health facility and by guiding the client to plan for the facility visit, using prompts such as "How will you get to the clinic? Can someone go with you?" While the CHW may facilitate disclosure if requested, the CHW will never share individual results with others.

Specification of intervention components In households assigned to the Intervention only, the following procedures will take place:

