1. The test statistic is the effect regression coefficient from a mixed-effects logistic regression model
2. Alpha = 0.05
3. Power = 90%
4. The proportion consenting to testing in the control group will be 0.85
5. The proportion consenting to testing in the intervention group will be 0.98 (a difference of +0.13 vs the control group).
6. An average of two household contacts will be eligible for HIV testing per household. The intra-class correlation (ICC) will be 0.59.

The total number of households needed is sensitive to the mean cluster size. Under the preceding assumptions, the necessary number of households may range from 152 if the mean number of eligible contacts per households is 2 to 138 if the mean number of contacts per household is 3. The total

number of households needed is also sensitive to the ICC. Sample size estimates assuming a range of possible ICC values, ranging from the value observed during the preliminary research (0.59) to higher values (0.65, 0.70), are not presented here although considered by the study team. Finally, the total number of households needed is sensitive to the baseline (control group) proportion of tests accepted. Sample size estimates assuming three possible baseline testing rates (75%, 80%, and 85%) in control group households have been considered. We will plan an interim blinded power analysis by an external biostatistician to readjust sample size targets as necessary for actual mean cluster size and ICC after enrolling the first 100 households.

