All patients and their household contacts will receive a verbal invitation to participate in accordance with National TB guidelines. Additionally, all willing and eligible index patients and their household contacts will be asked to review the research study information sheet /verbal informed consent document outlining all study related activities, then provide verbal consent to participate in the study. Lay health workers trained in administering informed consent procedures, Human Subjects' Protection and Good Clinical Practice will carry out and document all verbal informed consent encounters. For participants under age 18 who do not meet the definition of an emancipated minor, permission to participate will be obtained from a parent or legal guardian. Among index patients, children aged 14-17 must provide assent to participate after their parent provides permission. Among contacts, only household members 15 years of age or older will be eligible for HIV testing; those aged 15-17 must provide assent to participate after their parent provides permission.

After a participant agrees to participate and/or a parent provides permission, the lay health worker will carry out the routine contact investigation procedures, recording clinical and demographic information about the patient on an electronic tablet. This information will include names and ages of all household members, contact telephone numbers for the index patient and a treatment supporter.

7. **Evaluation of Subject(s) Capacity to Provide Informed Consent/Accent:** Indicate how the personnel obtaining consent will assess the potential subject's ability and capacity to consent to the research being proposed.

8. **Non-English Speaking Subjects:** Explain provisions in place to ensure comprehension for research involving non-English speaking subjects. If enrollment of these subjects is anticipated, translated copies of all consent materials must be submitted for approval prior to use.

Subjects who do not speak English or Luganda will be excluded from this formative study. All LHWs administering study protocol will be fluent in both English and Luganda. All consent forms will be available in both English and Luganda and will be administered in the language of preference.

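### The fixed script for a positive oral HIV test presents a diagnosis and leaves out the confirmatory blood test that the protocol requires for that result

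*Combined protocol and SAP*

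**What the plan says.** Two adjacent paragraphs of Section I.4, in the Aim 2 procedures, deal with a positive oral test.

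*HIV test results* defines a positive as "one line next to BOTH the C and T regardless of how faint". For that result, and also when no line appears at all (which the protocol calls unconfirmed), the community health worker (CHW) gives counselling and support "as well as a referral to the health centre for confirmatory capillary blood testing".

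*Referral protocol* applies to both arms: "Regardless of study arm, if the HIV test is positive or unconfirmed", the client is referred with a slip, and the referral is described as being for evaluation and care. As the first step, "the CHW will explain the result in direct, simple language". For a positive result the words are then fixed: "The test shows you have HIV. You need to go to the ART clinic", followed by an offer of support. After that the CHW hands over the slip and a phone number and helps the client plan a day and time to attend.

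Other parts of the plan refer to information whose content is not given. *HIV testing procedures* says "The CHW will then provide pre-test counselling". Section III.6 refers to a "verbal informed consent document outlining all study related activities".

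**The concern.** The plan treats a positive oral test as a result that still needs a blood test, yet the only disclosure wording it fixes is worded as a conclusion. A contact whose oral test is falsely reactive, and who hears the script as written, is told at home that they have HIV before the required check.

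This matters in this trial for three reasons. Section I.10 names psychological and social harm from disclosure as the primary risk to participants. The visit takes place in the household, and the CHW may help with disclosure on request, so an unconfirmed status could be shared with others that day. The blood test also happens only if the client attends the health centre. A client who heard only the script and did not attend would not know that the result needed checking.

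**Working it through.** No figure in the plan is at issue, so the check compares the two paragraphs and then looks for wording elsewhere that would close the gap.

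1. **Same result.** *HIV test results* covers a positive test, however faint the line. The script in *Referral protocol* is introduced as the explanation for a positive result. Both concern the same oral test, before any blood test.

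2. **Status of the result.** The first paragraph sends it for confirmatory capillary blood testing. On the plan's own terms it is not yet a confirmed diagnosis.

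3. **What the client hears.** The script attributes the finding to the test, states that the client has HIV and names the ART clinic. It does not say that the result is a first result, that it may change, or that a blood test follows.

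4. **Rest of that paragraph.** It covers the slip, the phone number, visit planning and privacy of results. It does not repeat the confirmatory test.

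5. **Rest of the document.** Confirmatory HIV testing is mentioned nowhere else. Other uses of *confirmed* concern the index patient's TB. Pre-test counselling, counselling after the result, the optional pictorial guide, the referral slip and the information sheet could all mention the blood test, but their wording is not available.

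6. **Reach.** The paragraph applies regardless of arm, so the same words are used in both.

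7. **Size.** A count of false-reactive disclosures needs the test's false-reactive rate. The documents give no sensitivity or specificity. The uptake assumptions in *Sample Size* (for example, "The proportion consenting to testing in the control group will be 0.85") help to say how many tests to expect, but not how many reactive results would be false. No count is therefore given, and the comparison in steps 1 to 5 does not need one.

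**The case against.** The strongest reply is that this is an omission in one sentence of a longer encounter. The script credits the statement to the test and does not say that the result is final or that treatment will start. The same visit includes counselling and a referral whose stated purpose is confirmation, and a CHW would ordinarily explain that purpose when handing over the slip.

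Much of this stands. The referral is intact, so nobody loses the confirmatory test. Nor can it be shown that clients are left uninformed, since the materials that might inform them are not reproduced. Naming the ART clinic is not itself a conflict, because nothing says that the blood test is done elsewhere.

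The wording itself does not survive the reply. Explaining the result is the first step and its words are fixed. Any mention of confirmation in later counselling would have to correct a statement already made, and one made in pre-test counselling would be followed by a sentence that does not reflect it. To a lay client, being told that the test shows they have HIV and that they must go to the ART clinic reads as a diagnosis.

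**Conclusion.** The point holds as a defect in participant information and safety: the script is wrong as written for a result that the plan itself sends for confirmation. This rests on the text alone and assumes only that CHWs use the words given.

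Four stronger readings are tempting, and the documents do not support them:

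- **That the confirmatory test has been dropped.** It has not. It is missing only from what the client is scripted to hear.
- **That a given number of contacts will be wrongly told they have HIV.** No test accuracy is given, so any count would come from assumed values.
- **That the trial's results are affected.** The script is common to both arms and enters neither the power calculation nor the 152-household target.
- **That 1-month linkage should be calculated over all reactive contacts.** Section I.1 defines linkage among new PLWH. A contact who attends and is found HIV-negative has no HIV care to link to, and that denominator could count them as a failure.

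**What to change.** In both arms, replace the script for a positive oral test with wording such as: *This oral test is reactive. It is a first result. You need a blood test at the health centre to confirm it. I will support you.* Keep the referral slip, phone number and visit planning as they are. Check that the counselling content, slip, pictorial guide and information sheet say the same.

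Section I.1 lists the yield of HIV diagnoses among the Aim 2 measures without saying whether it means reactive or confirmed results. If yield is reported, the two counts can be given separately, and contacts confirmed HIV-negative should not be counted as unlinked PLWH.

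The cost is a short script change and brief CHW retraining, with no change to design, sample size or analysis. The downside is that calling the result a first result may press clients less strongly to attend than telling them they have HIV. The slip, phone number and agreed day and time partly offset this.

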TB and HIV stigma scales Study CHWs will individually administer the short-form HIV-TB stigma scales to all study participants regardless of group using the CommCare application alongside a visual aid. These scales have a total of 13 items and were validated in the Uganda setting as part of the Aim 1 procedures. The scales will be administered first at the beginning of the home visit, then again at its conclusion. Each time, the CHW will briefly orient the participant to the response categories using a visual aid.

Documentation and Data management All enrollment procedures, household contact interviews and HIV testing details will be collected using CommCare. All forms will be available within a customized CommCare application that prevents common errors (such as not filling out a question etc.). Quality control procedures will include review of all study data collection forms for completeness and accuracy, including quality assurance testing of all validation and skip logic within the application, prior to study initiation. The US study coordinator will initiate reports on missing data and provide feedback to all study team members on the quality of quantitative data. All changes will be recorded using a data management google doc tracking sheet that contains information on the change, who made the change and a link directly to the location of the change on CommCare. Any duplicate cases (i.e. two cases for one index patient or contact) will be archived and similarly recorded.

Follow-up interview. At 3 months, the study LHW or a member of study team will contact a subset of households to schedule a follow-up visit or phone call if a second visit is unable to occur. The study LHW or a member of the study team will re-administer stigma scales to each participating member. Household members who are not present at the second household visit will be contacted by telephone to schedule a follow-up interview.

Sample Size.

During aim 2, we will distribute the stigma scales up to approximately 152 households containing approximately 304 household contacts with approximately 1:1 randomization (half in each study arm). We analyzed power for a 2-arm household-randomized, controlled trial using mixed models tests for two proportions in a two-level hierarchical design (household, contact). The assumptions and parameters within these calculations were based on data from Aim 1 and include:

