Analysis. In the Aim 2 analysis, our primary outcome is change in perceived HIV-TB stigma after following the first household contact tracing visit; the secondary outcome is uptake of HIV testing; we will descriptively assess linkage to care from both baseline data and intervention households. We will calculate descriptive statistics for participant characteristics, and test associations between characteristics and perceived/attributed household stigma. To test the hypothesis that invitation scripts that apply acceptance-optimized sequencing of oral test offers and prosocial messaging can decrease HIV stigma within households, we will evaluate change in HIV-TB stigma using cluster-adjusted dependent t-tests and fitting multilevel models with clustered standard errors. To test the hypothesis that prosocial messaging and theory-informed sequencing of HIV test offers can increase test uptake, we will compare testing uptake among the intervention households and pre-implementation households using cluster-adjusted chi-squared tests of proportion and by fitting multilevel logistic regression models. All hypothesis tests will be carried out at alpha of 0.05, corrected for multiple tests as appropriate. We will report household ICC for stigma as well as test uptake.

5. Genetic Testing N/A

6. **Subject Population:** Provide a detailed description of the types of human subjects who will be recruited into this study.

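### The household counts fit a cluster-adjusted test of two proportions, but the plan names a mixed-logistic coefficient without saying how it is tested, and it gives two comparators for uptake

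*Combined protocol and SAP*

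**What the plan says.** The Sample Size text for Aim 2 (Section I, item 4) says that power was analysed "using mixed models tests for two proportions in a two-level hierarchical design (household, contact". The assumptions that follow begin with "The test statistic is the effect regression coefficient from a mixed-effects logistic regression model". They continue with alpha 0.05 (sidedness not given), power 90%, control uptake 0.85, "The proportion consenting to testing in the intervention group will be 0.98", an average of two eligible contacts per household, and "The intra-class correlation (ICC) will be 0.59". The result is that "the necessary number of households may range from 152 if the mean number of eligible contacts per households is 2 to 138" with three contacts. The ICC is described only as the value seen in preliminary research. After 100 households an external biostatistician makes a blinded check "to readjust sample size targets as necessary for actual mean cluster size and ICC".

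The Analysis text of the same item says that "the secondary outcome is uptake of HIV testing". It adds that "we will compare testing uptake among the intervention households and pre-implementation households using cluster-adjusted chi-squared tests of proportion", alongside multilevel logistic models. Section I, item 13 (Statistical Considerations) lists the same two kinds of analysis by intention to treat, but compares intervention with control households. It also treats a household ICC above 0.2 as the level that calls for adjustment. Both places set alpha at 0.05, corrected for multiplicity where appropriate.

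Neither place says which analysis of uptake decides, how the coefficient's p-value is obtained, on which scale the ICC is defined, or what happens if an arm has no decliner.

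**The concern.** At 98% uptake, the intervention arm of 76 households with two contacts each (152 contacts) is expected to have 152 x 0.02, or about 3, decliners. So close to the boundary, a Wald test of a log odds ratio loses power. With no decliner at all, the coefficient has no finite estimate. An analyst who follows assumption 1 and reports a Wald p-value could therefore have clearly less than the stated 90% power, or no estimate to report.

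The unstated ICC scale also matters at the 100-household check, because a value from a mixed logistic model is not interchangeable with the one the formula expects.

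The comparator is a separate matter. A comparison with pre-implementation households would give up the protection of randomisation for this outcome.

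**Working it through.** **Inputs.** From the Sample Size text: 0.85 versus 0.98, alpha 0.05, power 90%, ICC 0.59, m = 2 or 3 contacts per household, allocation about 1:1. Two-sided testing is an assumption: it reproduces the counts, while one-sided testing gives 124 households at m = 2.

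**1. Reproducing the counts.** The pooled two-proportion formula, before clustering, gives

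n per arm = (1.96 x sqrt(2 x 0.915 x 0.085) + 1.2816 x sqrt(0.1275 + 0.0196))^2 / 0.13^2 = 94.62 contacts.

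With design effect 1 + (m - 1) x 0.59:
- m = 2: 94.62 x 1.59 / 2 = 75.2, so 76 per arm, **152** households (formula power 90.3%).
- m = 3: 94.62 x 2.18 / 3 = 68.8, so 69 per arm, **138** households (formula power 90.1%).

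Both match. The same design effect applied to a log-odds-ratio Wald formula gives 212 and 194, so the counts were not sized on the coefficient scale.

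**2. What 0.59 could mean.** The design effect treats it as the observed-scale correlation of the yes/no decisions. If it is instead a latent-scale ICC, the random-intercept SD is sqrt(0.59/0.41 x pi^2/3) = 2.176, which implies observed-scale ICCs of 0.354 at 85% and 0.185 at 98% uptake.

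**3. Chance of no decliner.** For a two-contact household, P(both accept) = 0.98^2 + ICC x 0.98 x 0.02. With ICC 0.59 this is 0.97196, and 0.97196^76 = 11.5%. With one random-intercept variance that gives 0.59 at 85% uptake, the intervention-arm ICC is 0.453 and the chance is 9.3%. On the latent reading it is 6.2%.

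**4. Power at 76 households of two contacts per arm.** The random-intercept logistic model was simulated with 12,000 trials per row, and the chi-squared test with 200,000.

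| Meaning of 0.59 | No decliner | Wald, all trials* | Wald, estimable trials | Likelihood ratio | Cluster-adjusted chi-squared |
|---|---|---|---|---|---|
| Observed scale, both arms | 11.5% | 69.5% | 79% | 96% | 94% |
| Observed scale in control, one random-intercept variance | 9.3% | 74% | 81% | 96% | 95% |
| Latent scale | 6.2% | 90% | 95% | 98% | 98% |

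*Trials with no decliner counted as non-significant.

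A 300-trial check of the first row with other mixed-model software gave 71% for Wald. At 138 households of three (2,000 trials), Wald power is about 78% with 0.59 on the observed scale in both arms and 95% on the latent scale.

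Type I error at nominal 5%, with both arms at 0.85 or 0.915, is 5.0-5.1% for chi-squared, 5.3-5.8% for likelihood ratio and 1.8-4.5% for Wald.

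**5. Unequal households.** With an assumed mix of sizes 1 to 5 averaging about two, the chi-squared test has 89.3-89.4% power.

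**6. The check at 100 households.** An observed-scale 0.59 at 85% uptake corresponds to a random-intercept SD of 4.074, a latent ICC of about 0.83 (0.835). Entered in the plan's formula, this gives 94.62 x 1.835 / 2 = 86.8, so 87 per arm or 174 households, with no real change in clustering.

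**7. Multiplicity.** If uptake shared a corrected alpha, the formula's power at 152 households would be 84% at 0.025 and 80% at 0.0167.

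**The case against.** The strongest reply is that the plan never mentions a Wald test. Assumption 1 names a coefficient, and a likelihood-ratio test of that same coefficient has 96-98% power. The Sample Size text also describes tests for two proportions, which is the formula that reproduces. This stands: the plan is under-specified, and the shortfall is conditional on a choice it leaves open.

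A reader might infer that, because 152 and 138 reproduce, 0.59 must have been an observed-scale estimate. They show only that 0.59 was entered in the design effect. A latent-scale estimate entered there gives the same counts, and then Wald power is about 90%.

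A reader might also take 70% as the trial's power for uptake. That figure scores every no-decliner trial as a failure, although the chi-squared test is already listed and rejects in over 99.9% of those trials. Using it there gives 0.695 + 0.115 = 81% or 0.740 + 0.093 = 83%. The lower figure also needs equal observed-scale ICCs in both arms, which a logistic model with a single random-intercept variance does not produce. The second row of the table is closer to assumption 1.

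Finally, the chi-squared result depends on household size. The plan says an average of two, and the margin over 90% disappears when sizes vary widely.

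None of this answers the conflict over the comparator.

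**Conclusion.** The mismatch is real but limited. The counts are right for a cluster-adjusted test of two proportions. They carry over to the named coefficient with a likelihood-ratio p-value, but not to a Wald p-value if 0.59 is truly observed-scale. In that case power at 152 households is about 70-74% over all trials, or 79-81% among estimable ones. On the latent-scale reading there is no material shortfall, though about 6% of trials still have no finite estimate. The documents do not settle the scale.

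They therefore do not support saying that the trial is underpowered for uptake or that 152 is the wrong number. Uptake is, besides, a secondary outcome of a pilot.

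These figures assume two-sided 0.05, two contacts in every household, no dropout, and beta-binomial or logistic-normal clustering. With widely varying household sizes, the chi-squared test is at about 89-90%.

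The contradiction between pre-implementation and control households needs no assumption and should be corrected in any case.

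**What to change.** 1. **Comparator.** Correct the Analysis text in Section I, item 4 so that uptake is compared between randomised intervention and control households, as in item 13.
2. **Deciding test.** Name one. The cluster-adjusted chi-squared test is preferable: it is already listed, the counts fit it, it holds its type I error, and it can be computed when an arm has no decliner. Apply it whatever the observed ICC, and reconcile this with the 0.2 threshold in item 13. The alternative is to keep assumption 1 with a likelihood-ratio p-value. Either way, do not use a Wald p-value for the mixed model, and state a rule for an arm with no decliner (for example: no point estimate, a one-sided profile-likelihood limit, and the difference in proportions).
3. **Sample Size text.** State that the 90% refers to that test of the secondary outcome, at two-sided uncorrected alpha 0.05, with about two contacts per household. State that the ICC is on the observed (proportion) scale, after confirming how 0.59 was estimated, and that the 100-household check uses the same scale.
4. **Multiplicity.** Say whether uptake is in a corrected family and, if so, restate the power as in step 7.

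The cost is wording only, with no added households. Keeping 90% under a corrected alpha would take 180 households (0.025) or 194 (0.0167) by the same formula. That is the sponsor's choice and not part of this fix.
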